2.3.2.3 Safety endpoints

At 75 ± 5 days following each transplant and 365 ± 14 days following the first and final islet transplant(s):

- The incidence and severity of adverse events (AEs) related to the islet transplant procedure, including: bleeding (>2 g/dL decrease in hemoglobin concentration); segmental portal vein thrombosis; biliary puncture; wound complication (infection or subsequent hernia); and increased transaminase levels >5 times upper limit of normal (ULN)
- The incidence and severity of AEs related to the immunosuppression including: allergy; reduction in glomerular filtration rate (GFR); increase in urinary albumin excretion; addition or intensification of anti-hypertensive therapy; addition or intensification of anti-hyperlipidemic therapy; oral ulcers; lower extremity edema; gastrointestinal toxicity; neutropenia, anemia, or thrombocytopenia; viral, bacterial, or fungal infections; and benign or malignant neoplasms
- The incidence of change in the immunosuppression drug regimen
- The incidence of immune sensitization defined by presence of anti-HLA (histocompatibility antigen) antibodies absent prior to transplantation

At 365 ± 14 days following the first islet transplant:

- The incidence of worsening retinopathy as assessed by change in retinal photography

2.4 Sample Size and Power Calculations

The primary outcome (favorable outcome) is defined as the dichotomous event HbA1c $<7.0\%$ at Day 365 AND free of severe hypoglycemic events from Day 28 to Day 365, inclusive, following the first islet transplant, with Day 0 designated as the day of transplant. The sample size assessment and power calculations are based on the rate of this favorable outcome.

Historical data were available on a total 131 islet alone transplants performed at the University of Alberta, the University of Miami, the University of Minnesota, the University of Pennsylvania, Emory University and Northwestern University. A summary of the observed favorable outcome rates are presented in the following table.

Table 1 - Favorable outcomes in the six participating clinical centers

Center	Number of Subjects Transplanted	Number with favorable outcome	Percent with favorable outcome
University of Alberta	68	49	72
University of Miami	21	17	81
University of Minnesota	20	16	80
University of Pennsylvania	9	6	75
Emory University*	8	7	88
Northwestern University*	5	4	80
Total	131	99	76

*co-investigator institutions

The observed favorable outcome rate is higher than 70% for all centers. To determine sample size, we constructed exact one-sided 95% confidence intervals [8] for selected observed favorable outcome rates. These lower bounds are listed in Table 2. For a selected observed rate, we can be 95% confident that the true (but unobservable) favorable outcome rate is at least as large as the lower bound of the confidence interval. With 95% confidence, any rate less than the tabulated endpoint will be excluded as a potential value for the true favorable outcome rate.

Table 2 - The highest favorable outcome to be ruled out with 95% confidence

	Sample Size			
	24	36	48	60
Observed Favorable Outcome Rate	Lower Confidence Bounds for Exact One-sided Binomial Confidence Intervals For Favorable Outcome Rate (%)			
10%	1.5	3.9	4.2	4.4
20%	8.6	9.5	11.8	12.0
30%	14.6	18.2	18.6	20.4
40%	24.6	25.3	27.7	29.3
50%	31.9	35.3	37.4	38.7
60%	39.7	46.0	47.5	48.6
70%	52.1	54.5	58.2	58.8
80%	61.1	66.6	67.2	69.6
90%	76.0	76.3	79.3	81.2

The best clinical judgment of the investigators is that a 50% or larger favorable outcome rate would be clinically meaningful. Based on past experience we would expect to

observe a rate larger than 70%. With a sample size of 48 transplanted subjects, 31 subjects (65%) would need to achieve a favorable outcome for the exact 95% lower confidence bound to rule out a 50% or lower true rate. (This result is not shown in the table; 65% favorable outcome rate of 48 subjects transplanted results in 31 successfully transplanted subjects). The proposed sample size is 48 subjects. Each participating center is expected to enroll at least 6 subjects.

Table 3 displays the probability that the study would conclude that the true favorable outcome rate is at least 50% for several selected values of the true favorable outcome rate. The tabulated probabilities are the power that a one-sided binomial test of the null hypothesis $H_0: p < 0.5$ versus the alternative hypothesis $H_a: p \geq 0.5$ would conclude that the true favorable outcome rate is at least 50% given that the selected value is the true underlying favorable outcome rate. These values are obtained by calculating the binomial probability that at least 31 out of 48 total enrolled subjects would achieve the favorable outcome given the true outcome rate.

Table 3- The power to rule out a favorable outcome rate that is less than or equal to 50% for the given true favorable outcome rate.

True Favorable Outcome Rate	Power to Rule Out Favorable Outcome Rate
10%	0.0000
20%	0.0000
30%	0.0000
40%	0.0005
50%	0.0297
60%	0.3111
70%	0.8359
80%	0.9962
90%	1.0000

This table shows that if the true favorable outcome rate is 70%, the power of concluding that the rate is over 50% is 0.8359 for a 5% level test.

3. General Analysis Definitions

3.1 Study Period and Visit Window Definition

3.1.1 Study Period

The trial consists of three periods: (1) the pretransplant period, which includes screening, enrollment, and wait list time; (2) the period that includes the islet transplant procedure(s); and (3) follow-up visits through 24 months following the final transplant. The study period of this trial is a 24-month follow-up after the final islet transplant. Subjects may undergo up to 3 transplants in the course of this study; the final transplant can occur not later than 8 months following the first transplant.

In the first period, individuals who meet the general inclusion criteria will be approached regarding participation in the study. After informed consent has been obtained, they will be formally enrolled into the study. Eligibility will be confirmed based on the results of the screening visit procedure detailed in Appendix 1 of the CIT-07 protocol. Enrolled subjects who meet the eligibility screening for the studies will be put on the waiting list for an islet transplant.

Once a compatible islet preparation becomes available, a subject's eligibility will be re-confirmed and eligible subjects will begin immunosuppression therapy on Day -2 (Day 0 is defined as the day of transplant).

During the post-transplant follow-up period, subjects may receive up to two additional transplants. After receiving his/her initial islet transplant, if a subject does not meet the criteria for insulin independence described in Section 4.1.2 of the CIT-07 protocol, but has either a basal or stimulated C-peptide level ≥ 0.3 ng/mL (0.1 nmol/L), s/he will be considered for a second islet transplant. A second islet transplant will be considered at 75 ± 5 days after the first islet transplant and when all required metabolic assessments are complete. If, after the second islet transplant, both basal and stimulated C-peptide levels remain <0.3 ng/mL (0.1 nmol/L), the recipient will be considered to have failed the endpoint, and immunosuppression will be managed as described in the protocol. A third islet transplant will be considered only if all the criteria described in Section 7.4 of the CIT-07 protocol are met. Islet transplant recipients who have completed 12 months of follow up after their first infusion will no longer be eligible for additional islet transplants under the CIT-07 protocol.

3.1.2 Visit Windows

The number of visits that occur before the first islet transplant will be determined by time on the waiting list and cannot be determined in advance. Screening tests and baseline measurements that are obtained during this period must be obtained within specified windows relative to the day of randomization, as described in Appendix 1 of the CIT-07 protocol (section 7). Following a transplant, up to 13 visits may be scheduled. Table 4 describes all visits, their scheduled times relative to the islet transplant, and the allowable visit windows.

Table 4 - Study assessment time points and visit windows

Time Points (days relative to transplant)	Visit Number	Visit Window (days relative to transplant)	Equivalent (weeks or months)
Screening	01	N/A	N/A
Waitlist/ Baseline	02	N/A	N/A
0	03	N/A	N/A
3	04	N/A	N/A
7	05	±3	W1
14	06	±3	W2
21	07	±3	W3
28	08	±3	W4
56	09	±7	M2
75	10	±5	M2.5
120	11	±7	M4
150	12	±7	M5
180	13	±7	M6
270	14	±14	M9
365	15	±14	M12

This follow-up schedule will restart with visit 03 on the day that a subsequent islet transplant is performed. There is also a visit scheduled 365 days after the initial transplant. The detailed activities for each scheduled follow-up visit are described in Appendix 1 of the CIT-07 protocol.

3.2 Study Population

The study population consists of individuals with T1D who meet the eligibility criteria for the trial described in Section 3 of the CIT-07 protocol. This section of the SAP describes three study populations. All efficacy analyses will be done on the ITT population. Parallel analyses will be done on the per-protocol population. Safety analyses will focus on the safety population.

3.2.1 Intent-to-Treat Population

All efficacy and safety analyses will be based on a modified ITT principle: any subject in whom protocol-directed therapy (*e.g.*, immunosuppression) is initiated will be included in the ITT population. Subjects who are randomized but for whom a protocol directed therapy is not initiated will be listed in the final study report but will not be included in the ITT population.

A subject who is randomized but never receives protocol-directed therapy will not be included in the analysis.

3.2.2 Per-Protocol Population

A per-protocol analysis will include all subjects who are randomized to CIT-07 and in whom the islet transplant procedure is initiated. The procedure will be considered initiated when the operator (*e.g.*, surgeon or interventional radiologist) has started the process of obtaining access to the portal vein (*i.e.*, entered the body with a needle or scalpel).

3.2.3 Safety Population

The safety population consists of any subject in whom protocol-directed therapy (*e.g.*, immunosuppression) is initiated. Subjects in this population might not receive an islet transplant.

3.3 Treatment Assignment and Treatment Groups

3.3.1 Treatment Assignment

Enrolled subjects who meet the eligibility criteria will be placed on a waiting list for a transplant. Once a compatible pancreas becomes available, the subject will be reevaluated to ensure that s/he satisfies all inclusion/exclusion criteria and therefore is still eligible for CIT-07 and the site-specific Phase 2 study. Eligible subjects will be randomized into either the CIT-07 or the site-specific phase 2 study. Note that this randomization is between protocols and not to treatment arms within a protocol. This randomization is being performed to avoid bias in the assignment of subjects to protocols. The treating center will be blinded to protocol assignments until the subject is ready for transplantation.

3.3.2 Treatment Groups

The treatment in CIT-07 is the islet transplant and its associated immunosuppression. This is a single arm, open label trial and everyone assigned to this protocol receives the same study treatment.

3.3.3 Center Pooling Method

The primary analysis assumes no between-center variability with regard to the favorable outcome resulting from the treatment. The data from all centers will be pooled without any adjustment for centers.

After the completion of CIT-07, it may be of interest to evaluate each center's individual favorable outcome rate. For this secondary analysis, a Bayesian random-effects model, allowing for the possibility of variability between centers, will be implemented. A detailed analysis plan for the Bayesian random-effects model with implementation code is described in Appendix 8.

3.4 Subject Disposition

The number of subjects enrolled and treated will be summarized and reported in the following categories:

- a. The numbers of subjects who are screened - total and grouped by center.

- b. The numbers of subjects who are excluded from study participation - total and grouped by center. The numbers will also be tabulated by the reason for exclusion.
- c. The numbers of subjects who are enrolled (sign informed consent for screening) - total and grouped by center.
- d. The numbers of subjects who are eligible for the transplant both after the enrollment and before the transplant, grouped by center.
- e. The numbers of subjects who are lost to follow-up, grouped by center and reason. (The rules for premature termination of study treatment are fully described in Section 5.7.2 of the CIT-07 protocol).

A list of all enrolled subjects (grouped by center) who are prematurely terminated from the study (withdraw consent or are lost to follow-up) will be provided. The list will give subject identification, the specific reason for termination, immunosuppression regimen and the duration of treatment before the termination.

3.5 Protocol Deviations

Major protocol deviations will be summarized by center and for the total study and grouped into the following categories:

1. Impacts the inclusion and/or exclusion criteria (PD1)
2. Involves consent violations (PD2)
3. Alters protocol-specified study therapy (PD3)
4. Impacts the ability of the Sponsor to evaluate the endpoints of the study (PD4)
5. Involves administration of prohibited medications (PD5)

The template of summary tables for the protocol deviations is provided in Appendix 6. Individual subjects with these protocol deviations will be listed with specifics on the deviation.

3.6 Demographic and Baseline Characteristics

3.6.1 Baseline Data

Baseline data collected for the ITT analysis consists of demographic information and medical/physical assessments during the waiting period for islet transplant. These data will be grouped into the following categories:

Demographic variables

- Age
- Sex
- Race (White, Black, Hispanic, Asian and Other)

Diabetes Control

- Insulin requirement (units/day)
- HbA1c

- Fasting and post prandial plasma glucose
- Fasting and post prandial C-peptide
- 90-minute C-peptide following consumption of Boost[®] or equivalent
- 90-minute glucose following consumption of Boost[®] or equivalent
- Number of severe hypoglycemic events in the last year
- MAGE score
- LI
- Clarke Score
- HYPO score
- β -score
- C-peptide/(glucose·creatinine) ratio

Body Habitus and Quality of Life

- Body Weight
- Height
- QOL Measures (defined in SAP section 3.6.5)

3.6.2 Statistical Analysis of Baseline Data

The number of subjects who do not meet the eligibility criteria will be reported, grouped by center. The numbers will be further broken down by the reasons for exclusion. These numbers and the corresponding rates will be reported in the summary table provided in SAP Appendix 7.

Descriptive statistics of baseline data, grouped by center, will be presented in a summary table. Continuous data will be summarized by mean, standard deviation, median, minimum, and maximum. Categorical data will be presented as numbers and percentages. The template of this table is described in SAP Appendix 1. Since the number of subjects randomized in each center is small, there will be no significance tests for the differences of the baseline data among the seven centers.

3.6.2.1 Analysis of demographic variables

3.6.2.1.1 *Age*

The distribution of age at baseline will be displayed as mean, standard deviation, median minimum and maximum.

3.6.2.1.2 *Sex and race*

Sex and race will be displayed as counts and percents.

3.6.3 Analysis of Diabetes Control Variables

Diabetic control variables include insulin requirement, fasting and post-prandial plasma glucose and C-peptide, glucose and C-peptide 90 minutes post Boost[®] (or equivalent) glucose challenge, number of hypoglycemic events in the last year, MAGE score, LI,

Clarke score, HYPO score, β -score, and C-peptide/(glucose·creatinine) ratio (the ratio of C-peptide to the product of glucose and creatinine).

The distribution of number of hypoglycemic events in the last year will be presented in tabular form.

The remaining diabetes control variables are all continuous scale variables and will be displayed as mean, standard deviation, median, minimum and maximum. The Shapiro-Wilk test will be used to test the normality of this continuous variable. If the hypothesis of normally distributed data is not rejected at the 0.05 significance level, the usual normal

95% confidence interval $\bar{x} \pm t_{0.025}^{n-1} \times \frac{S_x}{\sqrt{n}}$ will be constructed for the true mean μ . If the data

are not normally distributed, the transformations $y = f(x) = \log x$, \sqrt{x} and $1/x$ of these variables will be examined sequentially until we fail to reject the hypothesis of normality using the Shapiro-Wilk test at the 0.05 significance level. If a transformation is identified such that normality holds then the sample mean \bar{y} and sample standard deviation s_y will be calculated for the transformed variable. The 95% confidence interval will be constructed as

$$\left[f^{-1} \left(\bar{y} - t_{0.025}^{(n-2)} \frac{S_y}{\sqrt{n}} \right), f^{-1} \left(\bar{y} + t_{0.025}^{(n-2)} \frac{S_y}{\sqrt{n}} \right) \right].$$

If these transformations fail to achieve normality, the bootstrap method will be adopted. One thousand bootstrap samples from the original data set with replacement are obtained. For each bootstrap sample, the sample mean is calculated. The 2.5 and 97.5 percentiles, $p_{0.025}$ and $p_{0.975}$, will be identified from the 1000 bootstrap sample means. The interval $[p_{0.025}, p_{0.975}]$ will be reported as the bootstrap 95% confidence interval for the true mean.

3.6.4 Analysis of Body Habitus Variables

Body habitus variables include height, weight, and body mass index (BMI). BMI is computed as the ratio of weight to the square of height (kg/m^2). All three variables are continuous scale and will be analyzed in the same manner as described for continuous variables in the previous section.

3.6.5 Analysis of Quality of Life Variables

In this study, five QOL measures are considered. Two scales are obtained from the SF36 questionnaire (version 2). These scales are the Summary Physical Component score (SPC) and the Summary Mental Component score (SMC). Additional QOL assessments include the Overall Health Status (OHS) measure based on the European Quality of Life (EQ-5D) instrument, the Diabetes Distress Scale (DDS), and the Hypoglycemia Fear Scale (HFS) scales.

The SF36 scales will be standardized to the US population. The EQ-5D OHS questionnaire provides two sub-scales: the Behavior subscale that is based on 10 questions and ranges from 0 to 40 and the Worry subscale that is based on 13 questions. The scale is computed as the sum of the responses to the 13 questions and ranges from 0 to 52. The DDS is based on 17 questions rated on a 6 point Likert scales and ranges from

17 to 102. The HFS has two subscales: the Behavior scale which ranges from 0 to 40 and the Worry scale that ranges from 0 to 52.

All QOL scales are continuous and will be analyzed in the manner described in SAP section 3.6.3 for the continuous scale diabetes control variables. Each scale will be tabulated as mean, standard deviation, median, minimum and maximum. 95% confidence intervals will be computed in the manner described in SAP section 3.6.3.

3.7 Efficacy Analyses

3.7.1 Statistical Analysis of Primary Endpoint

HbA1c is the standard measure of glucose control and is used in all major studies as an endpoint for glycemic control. It has been valuable as a risk predictor of diabetes complications. However, since HbA1c is an integrated average, it does not provide information about the range of glucose values a subject experiences. This limitation is a rationale for also including hypoglycemic event occurrence as part of the primary endpoint and various glycemic excursion measures as secondary endpoints.

The primary endpoint for this study is the proportion of subjects with an HbA1c <7.0% at Day 365 AND free of severe hypoglycemic events from Day 28 to Day 365, inclusive, following the first islet transplant, with the day of transplant designated Day 0.

The primary analysis is designed to estimate the true rate of favorable outcomes at one year in subjects in the ITT population pooled over all centers. The proportion of favorable outcomes will be used as the point estimate. An exact one-sided 95% confidence interval will be constructed assuming an underlying binomial distribution for the target population as follows:

If r out of 48 total enrolled subjects achieve the favorable outcome, the exact one-sided 95% confidence interval is given by $p \geq p_L$ where p_L is the solution of the equation

$$0.05 = \sum_{x \geq r} \binom{48}{x} p_L^x (1 - p_L)^{48-x}.$$

0.05 =

The rates of favorable outcome and exact one-sided 95% confidence intervals will be computed for each contributing center.

This analysis will be conducted for the ITT population. The primary endpoint should be available for all treated subjects. An exception will be if a death occurs, if the subject withdraws consent to be followed, or if immunosuppression is begun but the subject never receives a transplant. In these cases the endpoint will be classified as failure to achieve a favorable outcome. Should the endpoint not be evaluated for a particular individual for other reasons, a failure will be imputed unless an evaluation is done at a time longer than one year after transplant, in which case, that later value will be imputed. All imputations will be reported with the primary analysis. The rates and the exact one-sided 95% confidence intervals for complete data and imputed data will be compared to ascertain the sensitivity of the imputation.

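### The only planned check of the primary imputation can miss that a positive result rests on a value obtained after one year, and the 'complete data' it compares against are not defined

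*SAP*

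**What the plan says.** SAP section 3.7.1 analyses the primary endpoint in the ITT population, pooled over centers, with a fixed denominator: "If r out of 48 total enrolled subjects achieve the favorable outcome" is the start of the rule. The interval is specified as follows: "An exact one-sided 95% confidence interval will be constructed assuming an underlying binomial distribution". Section 2.4 fixes what success requires with 48 subjects: "31 subjects (65%) would need to achieve a favorable outcome".

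Section 3.7.1 then treats unavailable endpoints in two groups.

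- **Named exceptions.** "An exception will be if a death occurs, if the subject withdraws consent to be followed", or if immunosuppression was started and no transplant followed. For these three: "In these cases the endpoint will be classified as failure to achieve a favorable outcome".
- **Any other reason.** A failure is imputed, except that a value obtained more than one year after transplant is used if there is one.

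All imputations are to be reported. The check is that the rates and exact one-sided 95% intervals "for complete data and imputed data will be compared to ascertain the sensitivity of the imputation". The section does not say which subjects make up the complete data.

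No other analysis tests the primary imputation. Section 3.7.8 is limited to secondary endpoints. The per-protocol analysis (section 3.2.2) changes the population, not the imputation.

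**The concern.** Only one of these imputation rules can favor the product: a later value counted as success. A check of the imputation should therefore ask what happens when that credit is withdrawn, and the plan's own default for a missing endpoint is failure. The complete-data comparison asks something else. It removes the subject altogether, which costs one success but also shrinks the denominator, so the bound falls by less than it would under re-scoring. Near the threshold the two methods can give opposite answers.

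The undefined term adds a second problem. The three named exceptions are all scored as failures, so leaving them out of the complete data can only raise the comparison rate. That can offset the drop from removing later-value successes and hide a dependence that would otherwise show.

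At stake is whether the reader of the final report is told that a conclusion near the threshold rests on substituted values.

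**Working it through.** **Inputs.** n = 48, one-sided alpha 0.05 and the exact binomial bound come from section 3.7.1. The rate to exclude (0.50), the threshold of 31 and the power table come from section 2.4. The SAP gives no expected number of deaths, withdrawals or later values, so the counts below are assumptions.

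**Formula.** The lower bound p_L for r successes in n solves 0.05 = P(X ≥ r | n, p_L). This is the 0.05 quantile of a Beta(r, n − r + 1) distribution. The result is positive if p_L > 0.50.

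**Reproducing the plan.** P(X ≥ 31 | 48, p) is 0.0297, 0.3111, 0.8359 and 0.9962 at p = 0.5, 0.6, 0.7 and 0.8. These match Table 3, including the sentence that "the power of concluding that the rate is over 50% is 0.8359 for a 5% level test". The bound is 0.4962 for 30/48 (p = 0.0557, fails) and 0.5173 for 31/48 (p = 0.0297, passes), so the threshold of 31 is confirmed.

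**Step 1: later-value successes only, nobody else dropped.** With r successes on 48, of which k come from later values, the planned check shows (r − k)/(48 − k). Re-scoring shows (r − k)/48.

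| ITT result | k | Planned check | Bound | Re-scored as failure | Bound |
|---|---|---|---|---|---|
| 31/48 (0.5173) | 1 | 30/47 | 0.5082 | 30/48 | 0.4962 |
| 31/48 | 2 | 29/46 | 0.4987 | 29/48 | 0.4752 |
| 31/48 | 3 | 28/45 | 0.4888 | 28/48 | 0.4545 |
| 32/48 (0.5387) | 2 | 30/46 | 0.5208 | 30/48 | 0.4962 |
| 32/48 | 3 | 29/45 | 0.5113 | 29/48 | 0.4752 |
| 32/48 | 4 | 28/44 | 0.5014 | 28/48 | 0.4545 |
| 32/48 | 5 | 27/43 | 0.4912 | 27/48 | 0.4340 |
| 33/48 (0.5603) | 3 | 30/45 | 0.5341 | 30/48 | 0.4962 |

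In every row re-scoring loses the conclusion. The planned check misses this at 31/48 with k = 1, at 32/48 with k = 2, 3 or 4, and at 33/48 with k = 3. It catches it at 31/48 with k = 2 or 3, and at 32/48 with k = 5. This step does not depend on how deaths are handled.

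**Step 2: the named exceptions also left out.** This is one possible reading of *complete data*.

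- 31/48 with two later-value successes: 29/46 = 0.4987, flagged. With one death also dropped, 29/45 = 0.5113, not flagged.
- 30/48, which fails the primary at 0.4962, with one death dropped: 30/47 = 0.5082 would appear beside it.

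**Step 3: dependence on the 95% level.** Section 4.1 says the final confidence coefficient will be adjusted for interim looks, by an amount not stated. The bound for 30/47 is 0.5005 at one-sided alpha 0.04 and 0.4983 at 0.0375; its p-value is 0.0395. At alpha 0.025 the bound for 31/48 is itself 0.4946, and the threshold moves to 32.

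**The case against.** The strongest reply has four parts.

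1. **The SAP does not say that complete data leave out deaths, withdrawals and never-transplanted subjects.** It calls these cases classified and only the others imputed, so an analyst could keep them as failures in both data sets. This stands. A reader might infer that they are dropped, because they are listed as cases where the endpoint is unavailable and the next sentence speaks of other reasons, but the text does not settle it. Step 2 is therefore conditional. Step 1 is not.

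2. **The check is neither blind nor one-sided.** This also stands. Removing later-value successes lowers the rate, and 29/46 and 28/45 would be flagged. One might infer that the comparison can never reveal dependence or always favors the product; the numbers contradict both. It can miss dependence, and dropping failures makes that more likely.

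3. **The comparison cannot rescue a failed trial.** Correct. Seeing 30/47 beside 30/48, a reader might infer that a failed trial becomes positive. Nothing in the SAP lets the complete-data interval replace the ITT result, which stays failed at 30/48.

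4. **All imputations are reported, so anyone can subtract later-value successes by hand, and a close result is an edge case if the true rate is 70% or more.** The first half is true, but a reconstruction left to the reader is not a prespecified analysis. The second half is fair as to likelihood. Still, the gap is not confined to one success at exactly 31/48, as the rows for 32/48 and 33/48 show.

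**Conclusion.** The point holds as a weakness of the sensitivity analysis, not of the primary analysis. As specified, the comparison can report a positive bound when the conclusion rests on later-value successes. The simplest case is 31/48 with one such success: 0.508 by the planned check against 0.496 when it is scored as failure. Leaving *complete data* undefined makes matters worse, because one permissible reading removes known failures and can turn a flagged result (29/46, 0.499) into an unflagged one (29/45, 0.511).

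This rests on two assumptions: that a subject with a substituted later value is not part of the complete data, and that the unadjusted one-sided 95% level applies. The examples are illustrations near the threshold. An interim adjustment could change which of them cross 0.50, but not the difference between deleting a later-value success and re-scoring it. This is a cheap improvement that goes further than defining a term, since re-scoring is a better check than the one planned.

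**What to change.** In section 3.7.1:

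1. State that death, withdrawal of consent and immunosuppression without transplant remain failures in every analysis of the primary endpoint.
2. Make the main sensitivity analysis the full ITT denominator with every later-value success re-scored as failure, using the same exact bound and confidence level as the final primary analysis.
3. Report the number of re-scorings needed to lose the conclusion. At the unadjusted level this is r − 30 for r ≥ 31 successes out of 48: one at 31, two at 32, three at 33. Set it beside the number of later-value successes actually used.
4. If a complete-data rate is still shown, define it as excluding only subjects whose endpoint is missing for other reasons, and present it as descriptive.

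The cost is a few lines of SAP text and one extra table row, with no new data. The downside is that the sensitivity figure may look less favorable than the one now planned.
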